- Patients' cytokines and chemokines levels prior to treatment, +2 and +4 weeks (+/- 3 days) post randomization
- Patient's gut microbiota diversity and composition prior to treatment, +3 day, +7 day, +2 weeks, +4 weeks, and +2 months post randomization

Safety endpoints

- Rates of adverse events associated with convalescent plasma infusion.
- Safety assessment will be performed on infusion day for the Treatment group (immediately post infusion), and for all patients on randomization day +3 and +7 days (by telephone, closest business day is acceptable), +2 weeks (+/- 3 days), +4 weeks (+/- 3 days).

Inclusion Criteria

Donor (see Appendix A)

- Age 18-60
- A history of a positive nasopharyngeal swab for COVID-19 or a history of positive antibody titer test.
- At least 14 days from resolution of COVID-19-associated symptoms including fevers.
- A negative nasopharyngeal swab (or similar test) for COVID-19
- anti-SARS-CoV2 titers $\geq 1:500$
- Adequate venous access for apheresis
- Meets donor eligibility criteria in accordance to Hackensack University Medical Center (HUMC) Collection Facility at the John Theurer Cancer Center (JTCC) if collecting at the JTCC, and all regulatory agencies as described in SOP 800 01 (Appendix A).
- Required testing of the donor and product must be performed in accordance to FDA regulations (21 CFR 610.40), and the donation must be found suitable (21 CFR 630.30)

Patient

- Patient age ≥ 30 years old, newly diagnosed with a COVID-19 infection with onset of first symptoms ≤ 96 hours.
- And least one other high-risk feature:
 1. Age ≥ 65

2. BMI 30 or above
3. Hypertension, defined as SBP above 140 or DBP above 90, or requiring medication for control.
4. Coronary artery disease (history, not ECG changes only)
5. Congestive heart failure
6. Peripheral vascular disease (includes aortic aneurysm \geq 6 cm)
7. Cerebrovascular disease (history of CVA or TIA)
8. Dementia
9. Chronic pulmonary disease
10. Liver disease (such as portal hypertension, chronic hepatitis)
11. Diabetes (excludes diet-controlled alone)
12. Moderate or severe renal disease defined as having a GFR $<$ 60 mL/min
13. Cancer (exclude if \geq 5 year in remission)
14. AIDS (not just HIV positive)

Patient exclusion criteria

- History of severe transfusion reaction to plasma products
- Need for oxygen supplementation
- Positive test for COVID-19 antibodies
- Chemotherapy-induced neutropenia (ANC $<$ $0.5 \times 10^3/\text{mcL}$)

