2.2 Secondary objectives

- Time to symptoms resolution
- Duration of hospitalization
- Overall survival
- Rate of virologic clearance by nasopharyngeal swab at 2 and 4 weeks.
- Evaluation of donor parameters including nasopharyngeal swab positivity and titers levels
- Evaluation of the impact of donor titers level on efficacy.
- Patients' anti-SARS-CoV2 titer assessment pre-infusion for the Treatment group, +2 weeks (+/- 3 days), +4 weeks (+/- 3 days) and +2 months (+/- 5 days). Randomization day will be designated at day 0.

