3.1 Donor

Donors and donor products may be collected under IND 19824 as all aspect of donor and product handling is identical.

- Age 18-60
- A history of a positive nasopharyngeal swab for COVID-19 or a history of positive titer test.

- At least 14 days from resolution of COVID-19-associated symptoms including fevers
- One negative nasopharyngeal swab for COVID-19 RNA
- Adequate venous access for apheresis
- Anti-SARS-CoV2 titer titers $\geq 1:500$
- Meets donor eligibility criteria in accordance to regulatory requirements and Hackensack Meridian Health SOP 800 01 “COVID-19 Convalescent Plasma Procurement” (Appendix A).
- Required testing of the donor and product must be performed in accordance to FDA regulation 21 CFR 610.40, and the donation must be found suitable (21 CFR 630.30) (See Appendix A)

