8.3.3 Secondary Endpoints

- Time to Symptoms Resolution

Kaplan-Meier analysis will be used to describe time to symptoms resolution and the median time with 95% CI will be reported. Log-rank test will be utilized to compare the time to symptoms resolution between the Treatment and Control arms.

The time to symptoms resolution is defined as the time in days from therapies initiation to the first documented symptoms resolution as assessed by a local site. Patients whose symptoms are not resolved, or result in death, or lost follow-up on the designed follow-up date, will be censored on that date.

- Overall Survival (OS)

Overall survival (OS) will be defined as the time in days from study entry to death. Patients who are alive on the date of closing follow-up will be censored on that date. All events of death will be included, regardless of whether the event occurred while the subject was still taking new therapies, or after the subject discontinued study therapy. If a subject has not died, then the data will be censored according to the following rule: if the subject was lost to follow-up, then data will be censored at the last study visit, or the last contact date, or the date the subject was last known to be alive, whichever is later. If the subject was not lost to follow-up, then data will be censored at the last study visit or the last contact date, whichever is later.

OS will be estimated by Kaplan-Meier methodology, and median OS with 95% CI will be reported. And the OS between the Treatment and Control arms will be compared by Log-rank test.

- Rate of Virologic Clearance

The rate of virologic clearance by nasopharyngeal swab at 2 weeks and 4 weeks will be summarized by frequency (%) and compared between two randomized arms by Mantel-Haenszel test. The marginal model will be fitted to the rate of virologic clearance at different time points to evaluate the main effect of randomized arms by using the generalized estimating equations method.

Viral clearance at a designed follow-up date is defined as the cycle threshold (Ct) of RT-PCT at that designed follow-up date 40.

- Evaluation of Donor parameters

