Donor parameters including nasopharyngeal swab positivity and antibody titer levels. Donor parameters will be summarized by frequency (%) for categorical parameters, and mean (SD) or median [IQR, interquartile range] for continuous parameters based on the data normality. The association between the donor parameters and the hospitalization rate will be checked by Mantel-Haenszel test for categorical donor parameters, and t-test or its non-parametric version for the continuous donor parameters. The logistic regression model will be built to evaluate the main effect of donor parameters on the hospitalization rate.

- Patients' Anti-SARS-CoV2 titer Assessment

Patients' anti-SARS-CoV2 titer will be assessed pre-infusion (for the Treatment group), +2 weeks (+/- 3 days), +4 weeks (+/- 3 days), and +2 months (+/- 5 days). The antibody titers at the designed follow-up date will be summarized by mean (SD) or median [IQR] and compared between the Treatment and Control arms by t-test or its non-parametric version based on the data normality. The mixed-effect linear model will be used to assess the association between antibody titers measures with the randomized arms.

- Baseline Characteristics

All baseline summary statistics and analyses will be based on characteristics prior to the initiation of study drug. Frequency and percentages for categorical variables and mean (SD) or median [IQR] for the continuous variables based on the normalization of the data.

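### If donor swab positivity means the screening swab, it cannot be tested against hospitalization because every collected donor screened negative; the donor-titer model, which can be run, makes no allowance for shared donors

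*Combined protocol and SAP*

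**What the plan says.** Section 2.2 lists as a secondary objective "Evaluation of donor parameters including nasopharyngeal swab positivity and titers levels". A separate item in the same list concerns the effect of donor titer on efficacy.

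Section 8.3.3 turns these into analyses. It names the variables as "Donor parameters including nasopharyngeal swab positivity and antibody titer levels". After a descriptive summary, it states: "The association between the donor parameters and the hospitalization rate will be checked by Mantel-Haenszel test for categorical donor parameters". A t-test or its non-parametric counterpart is named for continuous parameters, and then: "The logistic regression model will be built to evaluate the main effect of donor parameters on the hospitalization rate". It does not say which swab result is the variable, and it names no method for recipients who share a donor. For virologic clearance, by contrast, the same section plans to "evaluate the main effect of randomized arms by using the generalized estimating equations method", and it names a mixed-effect model for repeated patient titers.

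Several donor rules bear on this:

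- Section 3.1 requires "One negative nasopharyngeal swab for COVID-19 RNA"; the Protocol Summary has "A negative nasopharyngeal swab (or similar test) for COVID-19". Both also set a titer floor of 1:500.
- Section 3.1 also requires "A history of a positive nasopharyngeal swab for COVID-19 or a history of positive titer test".
- Section 5.1.1 takes the swab and the antibody sample at visit 1 and lets only donors who meet every criterion go on to collection.
- Section 5.1 allows donor eligibility to follow later FDA updates.
- Section 5.1.2 permits repeat donation at intervals of 7 days or more, with the antibody test repeated each time, and collection as one large bag or two 200 mL bags.
- Section 5.2.2 allows a recipient two frozen units, or one if supply is short.

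**The concern.** An association test needs a covariate that varies. If swab positivity is the screening result, the entry rule removes all positives before any plasma is collected, so one of the two named donor parameters has nothing to estimate.

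The other parameter, titer, raises a different issue. The named tests and ordinary logistic regression treat recipients as independent by default, yet the donor rules allow one donor to supply several recipients, by repeat donation or by splitting the two bags of one donation. If those recipients' outcomes are correlated, standard errors for donor factors come out too small. This paragraph is also the only place in 8.3.3 that serves the titer-efficacy objective, so its result may be read as evidence on whether titer matters.

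**Working it through.** **Inputs.** 153 patients per arm (8.2) and 8% hospitalization under Treatment (8.1). The plan gives no sample size, power or precision for the donor analysis, so there is no figure of that kind to reproduce. The primary design behind the 153 does reproduce: simulating the stated boundaries at 51, 102 and 153 per arm gives a type I error of 0.050 and power of about 0.80 for 8% against 18%.

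**1. Screening swab.** Let n1 be recipients of plasma from swab-positive donors, n0 the others, m1 admissions, m0 non-admissions, and N their total. Under 3.1, n1 = 0.

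- The Mantel-Haenszel variance for one table is n1·n0·m1·m0 / [N²(N − 1)] = 0. The observed count equals its expectation (0 = 0), so the statistic is 0/0. Stratifying does not help, because n1 = 0 in every stratum.
- Logistic regression has two columns, an intercept of ones and a swab column of zeros. The matrix has rank 1 for 2 parameters, so the swab coefficient is not identified at any N.

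**2. Swab history.** A past positive swab versus entry on antibody history alone can vary between accepted donors. Assume that 5% to 50% of 153 recipients have donors with antibody history only, with 8% admitted overall. Two-sided 5% power is then about 15% to 24% for an odds ratio of 2 and about 30% to 48% for an odds ratio of 3.

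**3. Titer.** Expected Treatment admissions:

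- full size: 153 × 0.08 = 12.2
- stop at stage 2: 102 × 0.08 = 8.2
- stop at stage 1: 51 × 0.08 = 4.1

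With 12 admitted and 141 not, the standardized difference detectable with 80% power (two-sided 5%) is (1.960 + 0.842) × √(1/12 + 1/141) = 2.802 × 0.3007 = 0.84. The analysis is feasible but coarse. The 8% belongs to the 21-day window in 8.1, whereas 8.3.1 defines the endpoint at 10 days; a lower 10-day rate would mean fewer events.

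**4. Shared donors.** The documents give neither the number of recipients per donor (m) nor the intraclass correlation (ICC). For a covariate constant within donor, the design effect is DE = 1 + (m − 1) × ICC, and unadjusted intervals are too narrow by 1 − 1/√DE.

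| m (assumed) | ICC (assumed) | DE | Correct interval wider by | Unadjusted interval too narrow by |
|---|---|---|---|---|
| 3 | 0.05 | 1.10 | 4.9% | 4.7% |
| 5 | 0.10 | 1.40 | 18.3% | 15.5% |

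Over a wider assumed range, the actual level of a nominal two-sided 5% test runs from 0.051 (m = 2, ICC 0.01) to 0.206 (m = 8, ICC 0.20). These are worst-case values, because titer is re-measured at each donation and so need not be constant within donor.

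**The case against.** The strongest reply is that the plan never says the screening swab is meant. Section 3.1 admits donors on a past positive swab or a past positive antibody test, so swab history can differ and can be tested, and 5.1 lets the eligibility rules change. This stands as far as it goes: the term is empty only under the screening-swab reading and the criteria as written. That reading is the more natural one, since 5.1.1 lists swab and antibody test together at visit 1, but the text does not settle it. Either way the variable needs a definition.

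A reader might go further and infer that the whole donor analysis, or the secondary objective, cannot work. The documents do not support that. The objective in 2.2 is an evaluation of donor parameters and is not confined to accepted donors; a descriptive summary over everyone screened already fits 8.3.3. The 1:500 rule is a floor: titers above it still vary, and restricting a covariate's range costs precision without making its effect inestimable.

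On clustering, the objection is that repeat donation is only permitted, that recipients per donor are unknown, and that the plan does not assert independence. All true. What remains is that the named methods assume independence unless something else is specified, and for donors nothing is. With about 12 events, sampling error may well outweigh a 5% to 15% error in interval width. Clustered variance is also not automatically safe here: 3 to 5 recipients per donor means roughly 31 to 51 donors (153/5 to 153/3), few enough for uncorrected robust standard errors to be too small.

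**Conclusion.** The point holds in limited form. Under the criteria in 3.1, an association between screening-swab positivity and hospitalization is not estimable. If swab history is meant, the comparison is estimable but weak, and the plan should say so. The donor-titer analysis is estimable on about 12 expected admissions, with no provision for shared donors. The size of that second problem is unknown: about 5% to 15% too narrow under the assumed 3 to 5 recipients per donor and ICC of 0.05 to 0.10, in the worst case of a donor-constant covariate, and negligible if few recipients share a donor. Severity is low, because this is a secondary analysis and the primary comparison is untouched.

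**What to change.** In 8.3.3, under donor parameters:

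1. State which swab result is meant. If it is the screening swab, report it descriptively over all donors screened under this protocol and remove it from the Mantel-Haenszel test and the logistic model. If it is past positive swab versus antibody history only, say so and keep it, labelled as a low-power comparison.
2. Fit the titer-hospitalization model in Treatment-arm patients who received plasma. Control patients can receive plasma only after admission (5.2.5), that is, after the outcome.
3. Use the titer of the donation actually infused, and state a rule for the titer and cluster of a recipient whose two units come from different donors.
4. Use donor-clustered variance with a small-sample correction, since events and donors are few.

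The cost is SAP wording and a donor identifier in the analysis dataset. Visit 1 swabs and titers are already collected for donors screened here; screening results for donors enrolled under IND 19824 may not be, hence the restriction in item 1. Intervals for titer will generally be slightly wider.

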8.3.4 Exploratory

- Descriptive statistics will be used to characterize the patients' cytokines, chemokines, plasma products (mannose-binding lectin (MBL), procalcitonin (PCT), C-reactive protein (CRP), human neutrophil lipocalin (HNL), annexin V, surfactant protein D (SP-D), microRNAs) and gut microbiome at pre-infusion treatment day, + 3 and +7 days (gut microbiome), +2 and +4 weeks (+/- 3 days) and +2 months (gut microbiome) post randomization. Frequency and percentages for categorical variables and mean (SD) or median [IQR] for the continuous variables based on the normalization of the data.

Univariate test will be performed in terms of identifying the association between exploratory objective and the hospitalization rate, Mantel-Haenszel test for categorical variables, and t-test or its non-parametric version for the continuous variables based on the normalized of the data. Analysis of the exploratory objectives will primarily be descriptive.

P-value less than 0.05 will be considered significant. All statistical analyses will be performed using RStudio (Version 0.99.902) and SAS (Version 9.4).

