5.2 Patient procedures and evaluation (see Appendix B)

Patients may be screened, enrolled and randomized remotely. The day of randomization will be designated as day 0 for both Treatment and Control groups. Patients randomized to the treatment arm will need to be seen on the day of infusion which should occur within 48 hours of randomization and be within 96 hours of symptom onset.

5.2.1 Day 0. May be done remotely.

- Screening
- Informed consent must be obtained before performing study related activities (can be from healthcare proxy if subject unable to provide consent due to medical status)
- Baseline Evaluation (at screening)
 1. Demographics (age, sex ethnicity, race)
 2. Medical history
 - a. Date of onset of COVID-19 symptoms
 - b. Date of positive test
 - c. Acute and chronic medical conditions described in the eligibility criteria 3.2.
 - d. Charlson Co-morbidity Index calculation
 3. COVID-19 symptom screen (Y/N)
 - a. Fever (T Max)
 - b. Cough
 - c. Shortness of breath
 - d. Ageusia and/or anosmia
 - e. Myalgias
 - f. Headache
 - g. Other symptoms that the patient attributes to their COVID-19 infection
 4. Documentation of positive nasopharyngeal COVID-19 testing.
 5. Determination of eligibility as per inclusion/exclusion criteria
 6. Randomization

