5.2.2 Plasma infusion day

Patients randomized to the treatment arm will need to be seen on the day of infusion which should occur within 48 hours of randomization and be within 96 hours of symptom onset.

Study plasma administration will be allowed for the Control arm after hospital admission if requested by the patient's medical team.

- On the day of infusion, blood will be drawn for:
 1. Inflammatory markers

- a. D-Dimers
 - b. Ferritin
 - c. CRP
- 2. Serological testing: anti-SARS CoV-2 titers
- 3. Exploratory blood test for genomics (optional)
- 4. Exploratory blood test for cytokines/chemokines (optional)
- 5. Rectal swab for gut microbiome analyses, to be sent to the CDI if possible
- 6. CBC
- 7. Complete chemistry
- 8. ABO Rh

- Procedure:
 - 1. A single unit of approximately 400-500 mL of liquid fresh plasma or 2 units of fresh frozen plasma for a total of approximately 400 mL will be transfused at an approximate rate of 50 mL per hour x 30 minutes, then the rate may be increased up to 150 mL per hour until completion. If plasma availability does not allow for 2 units of FFP, a single unit may be administered.
 - 2. If possible, 10mL of plasma will be collected for research from the infusion line and sent to the CDI
 - 3. The infusion may be slowed or stopped as per investigator's decision for minor transfusion reactions only. The transfusion will be discontinued for any transfusion reactions other than minor allergic reactions.
 - 4. An investigation will be initiated when there are signs of a systemic transfusion reaction.
 - 5. Premedication 30 – 60 minutes prior to the infusion will include 100 mg hydrocortisone IV and may include acetaminophen 650 mg PO and diphenhydramine 25 mg IV. Diphenhydramine 25 mg IV and hydrocortisone 100 mg IV may be repeated as needed for an infusion reaction at the discretion of the investigator.
 - 6. Vitals signs should be monitored following Hackensack Meridian Health Blood and Blood Product Administration SOP guidelines:
 - a. Temperature, pulse, respirations, and blood pressure pre-infusion (within 30 minutes), 15 minutes after the start, every hour during, if a transfusion reaction is suspected or if there is any change in patient condition, post transfusion (5-15 minutes post)

5.2.3 Post enrollment day +3 and day +7 (or closest working day). May be done remotely.

- COVID-19 symptom screen by telephone (Y/N)
 - 1. Fever (T max)
 - 2. Cough
 - 3. Shortness of breath
 - 4. Ageusia and/or anosmia

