 - 5. Myalgias
 - 6. Headaches
 - 7. Other symptoms that the patient attributes to their COVID-19 infection

- New medical conditions, AE evaluation
- Safety assessment
- Rectal swab for microbiome at day +3 and day +7 to be sent to the CDI if possible.

5.2.4 Post enrollment: 2 weeks (+/- 3 days), 4 weeks and 2 months (+/- 5 days). Preferably in person.

- COVID-19 symptom screen (Y/N)
 1. Fever (T max)
 2. Cough
 3. Shortness of breath
 4. Ageusia and/or anosmia
 5. Myalgias
 6. Headaches
 7. Other symptoms that the patient attributes to their COVID-19 infection
- New medical conditions, AE evaluation
- Safety assessment
- Serological testing: anti-SARS CoV-2 titers if possible.
- Swab for COVID-19 testing at 2 weeks, and again at 4 weeks if week 2 is positive.
- Exploratory blood test for cytokines/chemokines at +2 and +4 weeks to be sent to the CDI if possible.
- Rectal swab for microbiome at +2 weeks, +4 weeks, and +2 months to be sent to the CDI if possible.

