8.1 Hypothesis

The primary objective is the hospitalization rate of patients with early COVID-19 infection at high-risk of admission. Suppose the hospitalization rate by 21 days from therapy initiation is 8% for the Treatment group (P_t) and 18% for the Control group (P_c). This phase II design will aim at the following hypothesis:

The design has a type I error rate at 0.05 with statistical power at least 0.80.

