8.3. Analysis Plan

8.3.1 Primary Endpoints

The primary endpoint of the phase II study is the hospitalization rate at 10 days from therapy initiation of patients with early COVID-19 infection at high-risk of admission. The hospitalization rate will be summarized by frequency (%) and compared between the Treatment and Control arms by Mantel-Haenszel test. There will be two interim analyses. Analysis reports will be provided to the DSMB to decide if there is a pronounced treatment effect or futility. A detailed interim analysis plan will be provided before the start of the interim analysis.

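### Section 8.3.4 tests patient biomarkers against hospitalization without requiring that the sample precede admission, although several planned samples fall after the outcome window has closed

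*Combined protocol and SAP*

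**What the plan says.** Section 8.3.4 opens with descriptive summaries of cytokines, chemokines, plasma-product analytes and gut microbiome. The times run from the pre-infusion sample through "3 and +7 days (gut microbiome), +2 and +4 weeks (+/- 3 days) and +2 months (gut microbiome) post randomization". It then adds an inferential step: "Univariate test will be performed in terms of identifying the association between exploratory objective and the hospitalization rate". The methods are the Mantel-Haenszel test for categorical variables and a t-test or its non-parametric counterpart for continuous ones, and p below 0.05 is called significant. The same section says the exploratory analysis is mainly descriptive.

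Section 2.3 defines the patient-level exploratory objectives together with their sampling times:
- cytokines/chemokines before treatment and at 2 and 4 weeks;
- microbiome before treatment, on days 3 and 7, at 2 and 4 weeks, and at 2 months.

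The outcome has two windows. Section 8.3.1 says: "The primary endpoint of the phase II study is the hospitalization rate at 10 days from therapy initiation". Section 8.1 says: "Suppose the hospitalization rate by 21 days from therapy initiation is 8% for the Treatment group".

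For blood sampling, section 5.2.2 lists an optional cytokine/chemokine draw on the infusion day. Section 5.2.4 lists "Exploratory blood test for cytokines/chemokines at +2 and +4 weeks to be sent to the CDI if possible". Section 5.2.1 (Day 0, which may be remote) lists no blood draw.

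**The concern.** A test of association between a biomarker and an outcome is easy to interpret only if the biomarker was measured before the outcome could have influenced it. Section 8.3.4 sets no such order: it has no restriction to pre-admission samples, no landmark, and no exclusion of patients already admitted.

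The protocol itself documents one way in which admission changes what is measured later. Sections 4.1, 5.2.2 and 5.2.5 let admitted Controls receive study plasma, given as in 5.2.2, which includes hydrocortisone premedication. A Control's 2-week or 4-week sample may therefore follow treatment that was given because of the outcome under test.

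At stake is how a p-value below 0.05 would be read. A late cytokine or microbiome difference between admitted and non-admitted patients could be taken as a marker of who will be admitted, when it may only mark who was admitted or who was sicker.

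**Working it through.** The plan gives no figure of its own on this point, and the sample-size calculation does not bear on it. The check is day arithmetic on two clocks: samples are counted from randomization, the endpoint from therapy initiation.

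**Inputs**
- Windows: 10 days (8.3.1) and 21 days (8.1).
- Delay from randomization to infusion: 0 to 2 days, from "day of infusion which should occur within 48 hours of randomization and be within 96 hours of symptom onset" (5.2).
- Sampling: 2 weeks ± 3 days and 4 weeks ± 3 days (8.3.4). Two months is taken as day 60 ± 5 days (the ± 5 is from 2.4 and 5.2.4; day 60 is my assumption).

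**Window close, in days from randomization** = window length + delay
- 10-day window: 10 + 0 to 10 + 2 = day 10 to 12.
- 21-day window: 21 + 0 to 21 + 2 = day 21 to 23.

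Therapy initiation is not defined for Controls. If their clock starts at randomization, the windows close on days 10 and 21.

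**Samples against windows**

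| Sample | Days from randomization | 10-day window | 21-day window |
|---|---|---|---|
| Day 3 (microbiome) | 3 | before close | before close |
| Day 7 (microbiome) | 7 | before close | before close |
| 2 weeks | 14 ± 3 = 11 to 17 | after close, except an overlap of 12 − 11 = 1 day at most | inside |
| 4 weeks | 28 ± 3 = 25 to 31 | after | after |
| 2 months (microbiome) | 60 ± 5 = 55 to 65 | after | after |

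The heading of 5.2.4 can be read as giving the 4-week visit ± 5 days. Its earliest day is then 28 − 5 = 23, still no earlier than the latest close of the 21-day window.

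**Post-outcome time points**
- 10-day window: cytokines 2 of 3 (2 and 4 weeks); microbiome 3 of 6 (2 weeks, 4 weeks, 2 months).
- 21-day window: cytokines 1 of 3 (4 weeks); microbiome 2 of 6 (4 weeks, 2 months).

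**The 2-week sample under the 21-day window.** The share of the window elapsed at sampling runs from (11 − 2)/21 = 43% to 17/21 = 81%. Section 1.4 reports that the site's admissions were mostly in the second week of illness. Assume admission on illness days 8 to 14 and randomization 0 to 4 days after onset. Admissions then fall on study days 8 − 4 = 4 to 14 − 4 = 10 for the latest randomized, and on days 8 to 14 for the earliest. Most would come before or around the 2-week visit.

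**Days 3 and 7.** These precede the close of either window but not necessarily a given patient's admission. On the same assumption, admissions can begin on study day 4, before the day 7 swab.

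**Measures not affected.** Plasma-product analytes come from the product or infusion line, and pre-infusion samples are drawn before therapy starts.

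**The case against.** The strongest reply is that the sentence setting up the tests names no time point. The times appear in the preceding sentence on description, the text speaks of association rather than prediction, and the section calls itself mainly descriptive. On that view this is an unspecified detail.

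Part of this stands. The plan makes no predictive claim, and a late difference between admitted and non-admitted patients is a legitimate description. No primary, safety or stopping decision depends on these tests, and many of the samples are optional or taken only if possible.

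The rest does not. The tests apply to the exploratory objectives, and 2.3 defines those with their late time points, so the plan as written does cover post-outcome samples. For cytokines the late samples are not a side issue: on the visit lists in 5.2, never-infused Controls have no cytokine sample before the 2-week visit. (The Appendix B schedule was not readable in the text available and should be checked on this.)

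A reader might infer more than the documents support:
- **That every exploratory measure is compromised.** Plasma-product analytes and pre-infusion samples are not.
- **That late associations would simply be effects of hospital care.** They could equally reflect underlying severity. Study plasma for admitted Controls, with its premedication, is documented; antibiotics are not mentioned. Hydrocortisone is not specific to admission either, since infused Treatment patients receive it too.
- **That the 2-week sample always follows the endpoint.** It does not under the 21-day window, nor quite always under the 10-day window.

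**Conclusion.** The point holds in limited form. Section 8.3.4 tests cytokines/chemokines and gut microbiome against hospitalization at the 0.05 level without requiring the sample to precede admission. The 4-week and 2-month samples follow the outcome under either window. The position of the 2-week sample depends on which window applies, so the post-outcome share ranges from 1 of 3 to 2 of 3 cytokine time points and from 2 of 6 to 3 of 6 microbiome time points. Associations from those samples cannot be separated from the consequences of admission or from severity.

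The counts rest on the stated visit windows and the 48-hour infusion allowance. Only the remark that most admissions would precede or surround the 2-week visit relies on the site's earlier experience and an assumed 0 to 4 days from onset to randomization. Because the analysis is exploratory, this is a cheap improvement and not a threat to the trial's main conclusions.

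**What to change.** In 8.3.4, limit tests against hospitalization to:
- plasma-product analytes;
- pre-infusion samples;
- a landmark analysis at each later sampling time, using only patients not yet admitted when sampled and testing against later admission within the window.

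The landmark condition must also apply to the day 3 and day 7 swabs, because a patient may be admitted before either. Present all other samples descriptively by arm and hospitalization status, without p-values. Reconcile the 10-day window in 8.3.1 with the 21-day window in 8.1, and define the start of the clock for Controls, so that the cut-off is fixed.

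The cost is a few sentences of text, fewer tests and less information. With no Day 0 blood draw listed for Controls, cytokine tests would rest mainly on the optional infusion-day sample in the Treatment arm. At the design rate and full enrolment that arm would have about 153 × 0.08 = 12 admissions. A 2-week landmark would add Controls only if the 21-day window is kept, with 21 − 17 = 4 to 23 − 11 = 12 days of window left (at most 21 − 11 = 10 if the Control clock starts at randomization). The plan should state this limitation.
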